3.3.1 Main diagnosis for trial entry

The trial will be performed in patients with chronic heart failure with an ejection fraction \leq 40%.

Please refer to [Section 8.3.1](#) (Source Documents) for the documentation requirements pertaining to the in- and exclusion criteria.

3.3.2 Inclusion criteria

1. Age \geq 18 years at screening. For Japan only: Age \geq 20 years at screening
2. Male or female patients. WOCBP^a must be ready and able to use highly effective methods of birth control per ICH M3 (R2) [[R09-1400](#)] that result in a low failure rate of less than 1% per year when used consistently and correctly. A list of contraception methods meeting these criteria is provided in the patient information
3. Patients with chronic HF diagnosed for at least 3 months before Visit 1, and currently in HF NYHA class II-IV
4. Chronic HF with reduced EF defined as LVEF \leq 40% per local reading (obtained under stable^b condition by echocardiography, radionuclide ventriculography, invasive angiography, MRI or CT). A historical LVEF may be used if it was measured within 6 months prior to visit 1 or the LVEF may be measured after study consent has been

Proprietary confidential information © 2019 Boehringer Ingelheim International GmbH or one or more of its affiliated companies

obtained. The LVEF must be documented in an official report prior to randomization.

^aA woman is considered of childbearing potential (WOCBP) if:

- having experienced menarche and
- not postmenopausal (12 months with no menses without an alternative medical cause) and
- not permanently sterilised (e.g., hysterectomy, bilateral oophorectomy or bilateral salpingectomy).

^bThe definition of “stable” is at the discretion of the investigator.

5. In addition to LVEF \leq 40%, patients must have at least one of the following evidence of HF:
 - a) If EF \geq 36% to \leq 40%: Elevated NT-proBNP at Visit 1 \geq 2500 pg/ml for patients without AF, OR \geq 5000 pg/ml for patients with AF, analysed at the Central Laboratory,
 - b) If EF \geq 31% to \leq 35%: Elevated NT-proBNP at Visit 1 \geq 1000 pg/ml for patients without AF, OR \geq 2000 pg/ml for patients with AF, analysed at the Central Laboratory,
 - c) If EF \leq 30%: Elevated NT-proBNP at Visit 1 \geq 600 pg/ml for patients without AF, OR \geq 1200 pg/ml for patients with AF, analysed at the Central Laboratory
 - d) For EF \leq 40% and documented HHF^c within 12 months prior to visit 1, elevated NT-proBNP at Visit 1 \geq 600 pg/ml for patients without AF and \geq 1200 pg/ml for patients with AF, analysed at the Central Laboratory.
6. Appropriate dose of medical therapy for HF (such as ACEi, ARB, β -blocker, oral diuretics, MRA, ARNI, ivabradine) consistent with prevailing local and international CV guidelines, stable for at least 1 week prior to Visit 1 and during screening period until Visit 2 (Randomisation) with the exception of diuretics stable for only one week prior to Visit 2 to control symptoms. The investigator must document in the source documents the reason why patient not on target dose per local guidelines
7. Appropriate use of medical devices such as cardioverter defibrillator (ICD) or a cardiac resynchronization therapy (CRT) consistent with prevailing local or international CV guidelines (refer also to exclusion #29)
8. Body Mass Index (BMI) $<$ 45 kg/m² at Visit 1 (Screening)
9. Signed and dated written ICF in accordance with Good Clinical Practice (GCP) and local legislation prior to admission to the trial

3.3.3 Exclusion criteria

1. Myocardial infarction (increase in cardiac enzymes in combination with symptoms of ischaemia or newly developed ischaemic ECG changes), coronary artery bypass graft surgery, or other major cardiovascular surgery, stroke or TIA in past 90 days prior to Visit 1
2. Heart transplant recipient, or listed for heart transplant
3. Currently implanted left ventricular assist device (LVAD)

^c The main reason for hospitalization must be HF as noted in the admission or discharge documentation. Documentation of HHF must be available in the source documentation at the site.

4. Cardiomyopathy based on infiltrative diseases (e.g. amyloidosis), accumulation diseases (e.g. haemochromatosis, Fabry disease), muscular dystrophies, cardiomyopathy with reversible causes (e.g. stress cardiomyopathy), hypertrophic obstructive cardiomyopathy or known pericardial constriction
5. Any severe (obstructive or regurgitant) valvular heart disease, expected to lead to surgery during the trial in the investigator's opinion
6. Acute decompensated HF (exacerbation of chronic HF) requiring i.v. diuretics, i.v. inotropes, or i.v. vasodilators, or LVAD within 1 week from discharge to Visit 1 (Screening) and during screening period until Visit 2 (Randomisation)
7. Atrial fibrillation or atrial flutter with a resting heart rate >110 bpm documented by ECG at Visit 1 (Screening)
8. Untreated ventricular arrhythmia with syncope in patients without ICD documented within the 3 months prior to Visit 1
9. Diagnosis of cardiomyopathy induced by chemotherapy or peripartum within the 12 months prior to Visit 1
10. Symptomatic bradycardia or second or third degree heart block without a pacemaker after adjusting beta-blocker therapy, if appropriate
11. Systolic blood pressure (SBP) ≥ 180 mmHg at Visit 2. If SBP >150 mmHg and <180 mmHg at Visit 2, the patient should be receiving at least 3 antihypertensive drugs
12. Symptomatic hypotension and/or a SBP < 100 mmHg at Visit 1 or Visit 2
13. Chronic pulmonary disease requiring home oxygen, oral steroid therapy or hospitalisation for exacerbation within 12 months, or significant chronic pulmonary disease in the opinion of the investigator, or primary pulmonary arterial hypertension
14. Indication of liver disease, defined by serum levels of either ALT (SGPT), AST (SGOT), or alkaline phosphatase above 3 x upper limit of normal (ULN) as determined at Visit 1
15. Impaired renal function, defined as eGFR < 20 mL/min/1.73 m² (CKD-EPI) or requiring dialysis, as determined at Visit 1
16. Haemoglobin (HgB) <9 g/dl at Visit 1
17. History of ketoacidosis
18. Major surgery (major according to the investigator's assessment) performed within 90 days prior to Visit 1, or scheduled major elective surgery (e.g. hip replacement) within 90 days after Visit 1
19. Gastrointestinal surgery or gastrointestinal disorder that could interfere with trial medication absorption in the investigator's opinion
20. Any documented active or suspected malignancy or history of malignancy within 2 years prior to screening, except appropriately treated basal cell carcinoma of the skin, in situ carcinoma of uterine cervix, or low risk prostate cancer (patients with pre-

- treatment PSA < 10 ng/mL, and biopsy Gleason score of ≤ 6 and clinical stage T1c or T2a)
21. Presence of any other disease than heart failure with a life expectancy of <1 years in the opinion of the investigator
 22. Patients who must or wish to continue the intake of restricted medications (see [Section 4.2.2](#)) or any drug considered likely to interfere with the safe conduct of the trial
 23. Current use or prior use of a SGLT-2 inhibitor or combined SGLT-1 and 2 inhibitor within 12 weeks prior to Visit 1 or during screening period until Visit 2 (Randomisation). Discontinuation of a SGLT-2 inhibitor or combined SGLT-1 and 2 inhibitor for the purposes of study enrolment is not permitted.
 24. Currently enrolled in another investigational device or drug study, or less than 30 days since ending another investigational device or drug study(s), or receiving other investigational treatment(s). Patients participating in a purely observational trial will not be excluded
 25. Known allergy or hypersensitivity to empagliflozin or other SGLT-2 inhibitors
 26. Chronic alcohol or drug abuse or any condition that, in the investigator's opinion, makes them an unreliable trial subject or unlikely to complete the trial
 27. Women who are pregnant, nursing, or who plan to become pregnant while in the trial
 28. Any other clinical condition that would jeopardise patients safety while participating in this trial, or may prevent the subject from adhering to the trial protocol
 29. Implanted cardioverter defibrillator (ICD) or a cardiac resynchronization therapy (CRT) within 3 months prior to Visit 1, or if there is an intent to implant ICD or CRT within 3 months of visit 1

3.3.4 Removal of patients from therapy or assessments

3.3.4.1 Removal of individual patients

This is a long-term outcome trial and every effort should be made by the site staff to encourage patients to remain in the trial and on trial medication unless medical condition substantially changes to alter the safety profile. If a patient is withdrawn from the trial the ExSC and the Sponsor should be informed immediately about each individual case.

Prematurely discontinuation of trial medication

For patients who prematurely discontinue trial medication all efforts should be made to observe these patients and ask them to continue to attend the scheduled visits until the end of trial. It is expected that all efforts are made to follow up on the collection of all adverse events, outcome events and concomitant therapy, and to have a complete dataset without missing data.

If a patient who prematurely discontinued trial medication is not willing to return to the predefined trial visits, at minimum a telephone call every 24 weeks (preferably every 12 weeks) and a telephone call at trial end will be required, to document the occurrence of

outcome events and vital status. If possible, other AE's and concomitant therapy changes since last visit must be recorded.

Every attempt must be made by the investigator to ensure patients continue participating in the trial during trial medication interruptions and after discontinuation of trial medication. Patients who prematurely discontinue trial medication are allowed to restart treatment, at any time if appropriate in the opinion of the Investigator. At every visit following trial medication discontinuation Investigators must consider if trial medication can be re-started.

Patients that are not actively taking trial medication may be less motivated to adhere to the scheduled trial visits. Investigators and site staff should work to detect early signs of losing interest and readily present such patients (not actively taking trial medication) with the following options to encourage continued participation:

- Option 1 Continue to attend regularly scheduled trial visits at the centre until the trial ends
- Option 2 Conduct all remaining trial visits over the phone
- Option 3 Discontinue participation in remaining trial activities but permit collection of vital status and CV outcome events at the end of the trial through the patient or alternative person designated by the patient (e.g., family, spouse, partner, legal representative, or physician) even if only by telephone. If possible, other AE's and concomitant therapy changes to be recorded. Sites should encourage the patient to return to the clinic for the final study visit.
- Option 4 Discontinue participation in remaining trial activities but permit collection of vital status at the end of the trial through the patient, alternative person designated by the patient, or through review of patient's medical information from alternative sources (e.g., doctor's notes, hospital records, etc.)

Patients will be asked to choose the most rigorous form of follow-up that they are willing to comply with.

A patient could be instructed to permanently stop the trial medication only after discussion with Investigator, if eligibility criteria are being violated, or if the patient fails to comply with the protocol (e.g. non-attendance at trial assessments).

Withdrawal of informed consent

A patient has the right to withdraw informed consent for participation at any time for any reason. However, withdrawal of consent from trial participation should be very rare and unusual. Because of this, the Investigator must be involved in the discussions with the patient regarding a withdrawal of consent. Additionally, the Investigator must discuss the withdrawal of consent with the Sponsor's/CRO's representative prior to stopping trial participation.

Early discontinuation of trial medication is not a criterion for withdrawal of consent for participation in the trial.

The right to withdraw informed consent at any time for any reason also applies to the optional informed consent to biobanking (including DNA sampling), which is separate from the consent for trial participation.

If the patient withdraws informed consent for participation in the trial, the trial will end for that patient. The patient should stop taking trial medication and should be asked to complete the end of treatment (EOT) visit and follow-up procedures as described in the [Flow Chart](#). Completing these procedures is strongly recommended for the patient's safety. Patients that withdraw informed consent will not be replaced.

Vital status must be collected at the end of trial for patients that withdraw consent from trial participation, if allowed by local regulations.

Patients lost to follow-up

If a patient is lost, every effort will be made by the Investigator and site staff to contact and locate the patient before the patient is declared lost to follow-up. Investigators and site staff must use every possible allowable means, according to local regulations, to locate patients who have missed visits. Efforts to contact the patient may include but are not limited to:

- Calling all numbers for patient and listed contacts (including in the evening and on weekends).
- Calling primary care physician, referring specialist and/or other listed physicians for more recent information, date of last office visit or to determine vital status.
- Sending an email and follow up with mailing certified letters (return receipt requested) to all known patient addresses and all listed contacts (e.g., relatives, friends, neighbours) that were provided by the patient.
- Reviewing patient's records and medical notes for any details of a hospitalisation, doctor's visit or other procedure that may indicate location or status of subject.
- Use Internet to search for possible contact information for the patient.
- Try reverse directory for phone numbers to get possible addresses and/or new contact details.
- Utilise social networking sites.
- Check local, regional, and national public records to locate the patient or search for vital status in accordance with local law.
- Consider home visit.
- Contact patient finder service.

Pregnancy

If a patient becomes pregnant during the trial, the trial medication will be stopped, the patient will be followed up during the trial and until birth or termination of the pregnancy (see further details in [Section 5.3.4.2](#)).

An excessive withdrawal rate can have a severe negative impact on the scientific value of the trial. The "Intention To Treat" analysis requires that all randomised patients be followed until trial end even if the trial medication was temporarily interrupted, discontinued or never started. Every effort should be made to keep the patients in the trial as scheduled. This includes careful patient selection and appropriate explanation of the trial requirements and

procedures prior to enrolment as well as an explanation of the consequences of premature withdrawal.

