5.1.2 Secondary endpoints

The key secondary endpoints, which are part of the testing strategy, are the following:

1. Occurrence of adjudicated HHF (first and recurrent)
2. eGFR (CKD-EPI)_{cr} slope of change from baseline

Other secondary endpoints (not part of confirmatory testing hierarchy on trial level) are the following:

- Time to first occurrence of chronic dialysis or renal transplant or sustained* reduction of $\geq 40\%$ eGFR (CKD-EPI)_{cr} or
 - sustained eGFR (CKD-EPI)_{cr} < 15 mL/min/1.73 m² for patients with baseline eGFR ≥ 30 mL/min/1.73 m²
 - sustained eGFR (CKD-EPI)_{cr} < 10 mL/min/1.73 m² for patients with baseline eGFR < 30 mL/min/1.73 m²

* An eGFR (CDK-EPI)_{cr} reduction is considered sustained, if it is determined by two or more consecutive post-baseline central laboratory measurements separated by at least 30 days (first to last of the consecutive eGFR values).

Chronic dialysis is regarded as chronic if the frequency of dialysis is twice or more per week for at least 90 days.

- Time to first adjudicated HHF
- Time to adjudicated CV death
- Time to all-cause mortality
- Time to onset of DM (defined as HbA1c $\geq 6.5\%$ or as diagnosed by the Investigator) in patients with pre-DM defined as no history of DM and no HbA1c ≥ 6.5 before treatment, and a pre-treatment HbA1c value of ≥ 5.7 and < 6.5
- Change from baseline in clinical summary score (HF symptoms and physical limitations domains) of the Kansas City Cardiomyopathy Questionnaire (KCCQ) at week 52
- Occurrence of all-cause hospitalisation (first and recurrent)

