5.3.7.2 Adverse event collection and reporting

AE Collection

The Investigator shall maintain and keep detailed records of all AEs in their patient files. The following must be collected and documented on the appropriate eCRF(s) by the Investigator:

- From signing the ICF onwards through the Residual Effect Period (REP), until individual patient's end of trial:
 - all AEs (serious and non-serious), Outcome events and all AESIs.
- After the individual patient's end of trial:

The Investigator does not need to actively monitor the patient for AEs but must report related SAEs and related AESIs of which the Investigator may become aware of by any means of communication, (e.g. phone call). Those AEs should however, not be reported in the eCRF.

The rules for Adverse Event Reporting exemptions still apply.

[figure not shown]

Figure 5.3.7.2: 1 Timelines for Adverse Event collection

The REP (timeframe after last dose of trial medication when measurable drug levels or pharmacodynamic effects are still likely to be present) is defined as 7 days after the last trial medication application. All AEs which occurred through the treatment phase and throughout the REP will be considered as on treatment. Please see [Section 7.3.4](#).

Events which occurred after the REP will be considered as post treatment events.

AE reporting to the Sponsor/CRO and timelines

The Investigator must report all non-exempted SAEs, AESIs and non-serious AEs which are relevant for the reported SAE or AESI, on the BI SAE form immediately (within 24 hours) to the unique entry point (contact details provided in the ISF). The same timeline applies if follow-up information becomes available. In specific occasions the investigator could inform the Sponsor/CRO upfront via telephone. This does not replace the requirement to complete and fax the BI SAE form.

With receipt of any further information to these events, a follow-up SAE form has to be provided. For follow-up information the same rules and timeline apply as for initial information.

Information required

For each AE, the Investigator should provide the information requested on the appropriate eCRF pages and the paper SAE form, if applicable. The Investigator should determine the causal relationship to the trial medication.

The following should also be recorded as an (S)AE in the eCRF and SAE form (if applicable):

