6.2.4 Early discontinuation of trial medication and trial termination

The EOT activities will be performed when a patient discontinues trial medication treatment permanently.

Note: The EOT activities should not be used for temporary interruptions of trial medication.

All patients will have a follow up visit 30 days following discontinuation of trial medication, irrespective whether they complete the treatment period or prematurely discontinue trial medication.

Patients who discontinue trial medication prematurely should thereafter continue to follow scheduled visits until trial end. For patients reluctant to attend the scheduled visits after prematurely discontinuing trial medication, some trial assessments may be negotiated with exception of collection of adverse events, outcome events and concomitant therapy.

Please refer to [Section 3.3.4.1](#) for detailed procedures to be followed in case a patient wants to stop trial medication.

In case of early trial termination (e.g. based on recommendation by the DMC), a reasonable timeframe to stop the trial (perform last patient visits) will be defined and communicated to the Investigators.

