### **6.8.3 Censoring**

The underlying principle is that the censoring date should be the last date a patient was known to be free of an endpoint event (e.g. free of each component of HHF + CV death).

For all endpoints except all-cause mortality and cause-specific death, patients without occurrence of a specific endpoint (composite endpoint or individual components) will be considered censored at the individual day of trial completion.

The individual day of trial completion will be the latest of:

- the last date the patient could be followed up for all non-fatal events as documented in the eCRF
- last onset of an AE or date of death
- onset dates of adjudicated events
- end of treatment
- last visit date (NYHA class, EQ-5D, KCCQ, pregnancy test, vital signs, ECG, or central laboratory- reported )

Censoring is considered independent from study drug intake.

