#### Events leading to lower limb amputation

A frequency table of patients with AEs leading to lower limb amputation as identified by the investigator by treatment, primary SOC and preferred term will be provided.

A separate table for AEs leading to lower limb amputation which are leading to discontinuation will be presented.

For events leading to lower limb amputations in addition to the ‘7-day-on-treatment approach’ all adverse events that occurred between first study drug intake up to trial completion will be presented (following censoring rules like non-fatal outcome events). For both approaches, SAEs will be presented.

Lower limb amputations (up to trial completion) will additionally be summarised by renal function, level of first amputation, reason for first amputation, history of PAOD, previous amputation and status of DM at baseline (DM / no-DM).

Patients with lower limb amputation will be listed.

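### Adverse events in off-drug patients followed by telephone: the protocol contradicts itself on what must be collected, and the SAP's trial-completion date can count uncollected time as event-free

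*Protocol*

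**What the plan says.** **Weaker collection text.** Protocol 3.3.4.1 sets a minimum for patients off trial drug who refuse visits: a call every 24 weeks and one at trial end, to establish outcome events and vital status. It then adds: "If possible, other AE's and concomitant therapy changes since last visit must be recorded". Section 6.2.3 says much the same of the trial-end call. Flow Chart footnote 2 also names only outcome events and vital status. Option 3 asks the patient to "permit collection of vital status and CV outcome events at the end of the trial", with other adverse events again where possible. Option 4 is vital status alone.

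**Stronger collection text.** The paragraph of 3.3.4.1 just before the minimum reads: "It is expected that all efforts are made to follow up on the collection of all adverse events, outcome events and concomitant therapy". Section 5.3.7.2 requires, from consent to the individual end of trial, "all AEs (serious and non-serious), Outcome events and all AESIs". Section 6.2.4 says that for patients reluctant to attend, "some trial assessments may be negotiated with exception of collection of adverse events, outcome events and concomitant therapy".

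**Censoring.** SAP 6.8.3 first states a principle: censor at the last date on which the patient was known to be free of the event. It then says that, deaths apart, patients without the endpoint "will be considered censored at the individual day of trial completion". That day is the latest of a list: the eCRF date to which all non-fatal events could be followed, last AE onset or death, adjudicated-event onset, end of treatment, and last visit.

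**Use.** All-cause hospitalisation, first and recurrent, is a secondary endpoint (Protocol 5.1.2). For lower limb amputation, SAP 7.8.1.3 adds a presentation in which "all adverse events that occurred between first study drug intake up to trial completion will be presented". SAP 7.8.1.4 does the same for fractures and urinary tract malignancies. SAP 7.8.1.1 runs time at risk for analyses to trial completion up to the individual day of trial completion. It also plans post-treatment incidence rates.

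**The concern.** A site can comply with 3.3.4.1 and 6.2.3 and still not ask about a hip fracture, an amputation or an admission for pneumonia. Health care resource use, the other record of hospitalisations, does not fill the gap, because Protocol 5.6.2 enters it at on-site visits only.

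If such a patient's time is nevertheless counted as observed, the numerator loses events that the denominator still covers. Rates for all-cause hospitalisation and for the late safety events come out too low. If one arm has more patients under limited follow-up, that arm also looks better than it should. The amputation table matters most here: amputation is an AESI, and the table to trial completion exists to show events that appear after drug has stopped.

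**Working it through.** **1. The collection texts side by side**

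| Place | Requirement for an off-drug patient |
|---|---|
| 3.3.4.1, 24-week and trial-end calls | outcome events and vital status; other AEs where possible |
| 6.2.3, trial-end call | the same |
| 3.3.4.1, Option 3 | CV outcome events and vital status at trial end; other AEs where possible |
| 3.3.4.1, Option 4 | vital status |
| 3.3.4.1, preceding paragraph | every effort to collect all AEs |
| 5.3.7.2 | all AEs to individual end of trial |
| 6.2.4 | AEs not negotiable |

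The first three rows cannot be squared with the last two. Section 3.3.4.1 does not define outcome events. All-cause hospitalisation is a listed endpoint, so a site might count it as one, but not under Option 3, which is limited to CV outcomes.

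**2. Does the SAP count the uncollected time?** Take a patient fully followed to month 6, then vital status only, who dies at month 24. The eCRF date for non-fatal events is month 6 and the death date is month 24. The latest of the two is month 24, so months 6 to 24 count as free of non-CV hospitalisation, amputation and fracture although nobody asked. A heart failure admission found at an Option 3 trial-end contact extends the date in the same way. Both results conflict with the principle stated at the head of 6.8.3. If no later listed date exists, time stops at month 6, as it should. The SAP does not say whether the eCRF date covers non-CV events.

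**3. Which analyses are reached?** The recurrent HHF model includes data after end of treatment for patients who did not complete treatment (SAP 7.5.1.1), and all-cause hospitalisation uses a similar model (7.5.2). Also reached are the AE presentations to trial completion and the post-treatment rates (7.8.1.1, 7.8.1.7). The general AE tables stop 7 days after last intake and are not reached.

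**4. Size, as illustration only.** The plan has no figure to reproduce. It gives a trial drop-out rate (under 1% per year), but no rate of stopping drug, of limited follow-up or of event capture. Let f be the share of person-time that is under limited follow-up yet stays in the denominator, and c the share of events still captured in that time. With the same true event rate throughout:

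- observed rate / true rate = 1 − f(1 − c)
- factor on the empagliflozin/placebo ratio = [1 − f_E(1 − c)] / [1 − f_P(1 − c)]

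Assumptions: mean follow-up T = 29 months (midpoint of the planned 20 to 38); a proportion d = 5 to 15% per year stop drug for good; a share s = 25 to 100% of them move to limited follow-up; c = 0 to 0.75. With λ = −ln(1 − d), f = s × [1 − (1 − e^(−λT))/(λT)].

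- Middle case (d = 10%, s = 0.5, c = 0.5): λT = 0.1054 × 2.417 = 0.2546; off-drug share = 1 − 0.2248/0.2546 = 0.117; f = 0.059; observed/true = 1 − 0.0586 × 0.5 = 0.971.
- Smallest effect (5%, 0.25, 0.75): f = 0.015; observed/true = 0.996.
- Largest effect (15%, 1, 0): f = 0.173; observed/true = 0.827.

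| f placebo / f empagliflozin | factor, c = 0.5 | factor, c = 0 |
|---|---|---|
| 5% / 5% | 1.000 | 1.000 |
| 6% / 4% | 0.98/0.97 = 1.010 | 0.96/0.94 = 1.021 |
| 10% / 6% | 0.97/0.95 = 1.021 | 0.94/0.90 = 1.044 |
| 4% / 6% | 0.97/0.98 = 0.990 | 0.94/0.96 = 0.979 |

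These figures let all limited-follow-up time stay in the denominator. Where the eCRF date does end the time, f is smaller. If off-drug patients have a higher event rate, the loss is larger.

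**The case against.** The strongest reply is that both documents already guard against this.

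- **Collection.** The calls in 3.3.4.1 are a minimum, and the demand for all adverse events stands directly above them. Patients are asked to choose the most rigorous follow-up they will accept. Under Option 2 all remaining visits are held by telephone and there is no weaker wording; the Flow Chart marks adverse events at telephone visits, and 6.2.2 directs those calls at hospitalisations and AEs. Section 5.3.7.1 requires new cancers to be reported however long after drug stop.
- **Censoring.** The list in SAP 6.8.3 opens with a date of complete non-fatal follow-up. The last-known-alive date is added for mortality only, so a vital-status contact does not by itself extend non-fatal time.
- **Renal composites.** A patient without an event is censored at the earliest component date, and laboratory components end at the last sample. These endpoints are therefore largely protected.
- **Consequence.** All-cause hospitalisation is exploratory, and the tables to trial completion supplement the on-treatment ones.

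Most of this stands. A reader might infer that adverse events are optional once drug has stopped; the three stronger texts rule that out, and what remains is a contradiction. A reader might also infer that all limited-follow-up time is counted in full. The SAP does not say so: it happens only when a later listed date overrides the eCRF date, or if that date does not cover non-CV events. The reply does not answer the contradiction itself, the override, or the undefined scope of the eCRF date.

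**Conclusion.** The point holds in a limited form. The protocol gives sites two incompatible rules for adverse events in off-drug patients who will not attend. The SAP's use of the latest date can turn time without ascertainment into event-free time, against its own censoring principle.

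The loss of events is a risk created by the wording, not something the documents show, and its size cannot be computed from them. Under the assumptions above, observed rates lie between 99.6% and 82.7% of the true rates (middle case 97.1%). With equal limited follow-up in both arms the ratio does not move. With differences of 2 to 4 percentage points of person-time it moves by about 1 to 4%.

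Missing non-CV adverse events do not affect the primary endpoint, recurrent HHF, eGFR slope or the on-treatment plus 7 days AE tables. Option 4 patients, for whom HHF is not collected either, raise a separate question that is not argued here. Severity is minor: a cheap improvement worth making.

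**What to change.** 1. **Protocol 3.3.4.1 and 6.2.3.** Bring them into line with 5.3.7.2 and 6.2.4. Make every hospitalisation, SAE, AESI (including lower limb amputation), fracture and malignancy a required question at the 24-week and trial-end calls, and at the Option 3 end-of-trial contact where the patient agrees. Align Flow Chart footnote 2. Option 2 needs no change.
2. **SAP 6.8.3 and 7.8.1.** For all-cause hospitalisation, and for AE analyses to trial completion or post-treatment, end time at risk for non-fatal events at the eCRF date of last complete non-fatal follow-up. State that this date covers non-CV hospitalisations and AEs, and that later listed dates do not override it. Leave the rules for HHF and CV outcomes as they are. The joint frailty likelihood in 7.5.1.1 uses one end time for both processes, so for all-cause hospitalisation allow the recurrent process to end before the terminal one. The all-cause mortality rule in 6.8.3 refers back to restrictions for withdrawn consent and loss to follow-up that the section does not contain; supply or delete them.
3. **Reporting.** Tabulate patients and person-time under Options 2 to 4 by arm, so that differential follow-up can be seen.

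The cost is a few questions in calls that already take place, a definition for an existing eCRF date, SAP wording, and a small loss of person-time in exploratory and safety analyses. Earlier censoring removes the distortion only if it is non-informative, which is a further reason for the tabulation.
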